2.0 Study Objectives

Specific Aim #1: Determine the concordance of imaging findings for fluciclovine-PET/MRI and mpMRI of the pelvis and prostate gland.

Hypothesis #1: Fluciclovine-PET/MRI will identify more regional lymph node metastases than mpMRI alone.

There have been numerous prior studies demonstrating the value of mpMRI for the locoregional staging for PCa. Prior studies in the setting of biochemical recurrence have demonstrated high sensitivity and specificity of fluciclovine-PET/CT for detection of recurrent disease in the prostate bed and extraprostatic disease.¹⁵ We expect the simultaneous acquisition of mpMRI and fluciclovine PET data to provide valuable preoperative staging information, with fluciclovine PET detecting metastatic disease in subcentimeter pelvic lymph nodes not identified with mpMRI alone. Additionally, fluciclovine-PET/MRI provides whole body staging in regions not evaluated by mpMRI and may detect additional distant metastases.

Specific Aim #2: Determine the correlation between organ-confined disease, lymph node metastases, extraprostatic extension, and seminal vesicle invasion on fluciclovine-PET/MRI with the expected frequencies of these metastases based on established nomograms and risk-prediction models as well as follow up fluciclovine-PET/MRI.

Hypothesis #2: Fluciclovine-PET/MRI will demonstrate metastases in the expected frequencies for patients with high-risk PCa and will regress with effective therapy.

For pretreatment patients with PCa, several clinical risk-predictors (including nomograms and Partin tables) utilize serum prostate-specific antigen (PSA), Gleason score, and clinical stage to predict organ-confined disease, the presence of extraprostatic extension, seminal vesicle invasion, and lymph node metastases.² Because majority of the high-risk prostate cancer population in this study will not undergo prostatectomy, nomograms and risk-prediction models combined with follow up fluciclovine-PET/MRI after therapy will be used as a surrogate for accuracy. If successful, this research plan will provide key data for further studies that will use histopathological confirmation as the reference standard.

Specific Aim #3: Measure changes in fluciclovine-PET/MRI at 6-12 weeks after initiation of therapy and correlate with serum PSA.

Hypothesis #3: Fluciclovine-PET/MRI parameters including fluciclovine uptake and fluciclovine-defined metabolic tumor volumes will change with effective therapy.

Resolution of fluciclovine-PET/MRI findings after therapy will also be used to help confirm true lesions on the pre-treatment imaging. If successful, this research plan will provide key data for further studies in for initial staging and monitoring therapy response that will use histopathological confirmation and patient outcomes as the reference standards.

For the post-treatment imaging, a repeat fluciclovine-PET/MRI study will be performed at 6-12 weeks months after initiation of therapy. The fluciclovine-PET and MR measurements will be compared between the pre- and post-treatment studies. Early detection of men at high risk for early treatment failure might undergo additional treatment prior to PSA rise from nadir. In the small number of patients in this study who undergo prostatectomy, the follow up fluciclovine-PET/MRI has the potential to detect residual disease that could then be treated with additional local therapy.

3.0 Investigational Plan

3.1 Study Design

- Prospective IRB-approved study enrolling patients with biopsy-proven high-risk prostate cancer for pretreatment fluciclovine-PET/MRI prior to the initiation of treatment and at three month follow-up
- All patients will undergo standard-of-care clinical evaluation and imaging workup with nuclear medicine bone scan and either CT of the abdomen and pelvis or MRI pelvis
- Majority of patients will be non-operative due to high-risk status, but participation in study does not exclude operative intervention
- Treatment team will initially be blinded to results of PET/MRI, but will be unblinded following standard-of-care imaging and formation of the initial treatment plan
- If study PET/MRI demonstrates a suspicious finding that may preclude a patient from operative intervention (in a patient being considered for surgery) or alter locoregional treatment (e.g. radiation therapy), the treatment team will be alerted to potentially investigate the finding further (i.e. additional imaging or biopsy)
- Findings on PET/MRI relayed to the clinical team may prompt further investigation on standard-of-care imaging and discussion in the genitourinary tumor board. If additional imaging and/or tumor board consensus indicates the need for biopsy, the biopsy can be billed to insurance as standard-of-care.
- A repeat fluciclovine-PET/MRI study will be performed at 6-12 weeks weeks after initiating therapy (typically radiation therapy, prostatectomy, and/or androgen deprivation therapy) at the time when serum PSA values are initially checked to establish response

3.2 Study Population

- Patients with high-risk biopsy-proven treatment-naïve prostate cancer

3.3 Inclusion Criteria

- High-risk biopsy-proven treatment-naïve prostate adenocarcinoma (Gleason score ≥ 8 and/or serum PSA > 20)

3.4 Exclusion Criteria

- Inability to tolerate or undergo PET/MRI
- Previous or current hematologic or lymphatic disorder (including leukemia, lymphoma, Castleman's disease, etc.)
- Recurrent prostate adenocarcinoma
- Known visceral, osseous, or extrapelvic metastases prior to fluciclovine-PET/MRI
- Known allergy to glucagon or gadolinium-based contrast

3.5 Withdrawal Criteria

- Given that enrollment in this study will involve two imaging exams, no withdrawal criteria will be used

3.6 Replacement of Patients

- Given that enrollment in this study will involve two imaging exams, no replacement of patients will be used

3.7 Study Duration

- Study enrollment and imaging will take place over 12 months

3.8 Safety Monitoring

3.8.1 Data and Safety Monitoring Plan

Patients will be informed of the extent to which their confidential health information generated from this study may be used for research purposes. Following this discussion, they will be asked to sign the HIPAA form and informed consent documents. The original signed document will become part of the patient's medical records, and each patient will receive a copy of the signed document. The use and disclosure of protected health information will be limited to the individuals described in the informed consent document. PET/MRI scans will be loaded into a separate password-protected image storage system that will not appear on the PACS utilized in clinical practice.

3.8.2 Ethical Considerations

Given that the study involves two imaging sessions with PET/MRI and the expected age of the enrolled adult patients, ethical concerns regarding additional radiation exposure are minimal. The only ethical consideration was the availability of the results of the study PET/MRI to the clinicians. Given that the PET tracer used (fluciclovine) is FDA-approved for a similar indication in the setting biochemical recurrence, it is highly likely that the tracer will behave in a similar fashion in these patients prior to therapy given similarities in tumor biology. Therefore, a suspicious lesion on the study PET/MRI is expected to correlate with metastatic disease. Therefore, if the PET/MRI demonstrates a suspicious finding, the treating clinician (including urology and radiation oncology) will be alerted, and the decision to pursue biopsy and/or alter the patients treatment plan will be based on standard of care imaging and consensus after presenting the case at the GU tumor board.

4.0 Study Procedures

4.1 Informed Consent Procedure

All participants must be provided a consent form describing the study with sufficient information for each participant to make an informed decision regarding their participation. Participants must sign the IRB-approved informed consent form prior to participation in any study specific procedure. The participant must receive a copy of the signed and dated consent document. The original signed copy of the consent document must be retained in the medical record or research file.

4.2 Patient Registration

Enrollment in the study will be available after the patient has been seen by their treating physician at UAB. The majority of these patients are expected to be seen in Urology clinic. However, all patients that meet enrollment criteria are eligible. Registration in the study will be performed by a research coordinator from the UAB Department of Radiology. Participation in the study is voluntary and choosing not to participate will not affect patient care in any way.

4.3 Initiation of Study

The PET tracer [¹⁸F]fluciclovine is FDA-approved for biochemically recurrent prostate cancer and readily available from commercial production sites. Additionally, UAB currently is performing clinical PET/MRI scans, including [¹⁸F]fluciclovine-PET/MRI. Therefore, the study can be initiated immediately following institutional and IRB approval.

4.4 Drug Information

[¹⁸F]fluciclovine is a non-natural amino acid radiotracer that is currently FDA-approved PET imaging agent for use in patients with biochemically-recurrent prostate cancer. The radiotracer targets both the LAT1 and ACST2 transporters, both of which are upregulated in prostate cancer cells. The dosage of radiotracer administered to the patient is 370 MBq (10 mCi) intravenously. This results in an effective dose of 8 mSv (800 mrem) to the patient, which is equal to 2.7 years of natural background radiation exposure (3 mSv/yr).

4.5 Patient Assessment

Identification and workup of patients prior to potential enrollment in the study will follow standard-of-care procedures per the treating physician (urology, radiation oncology, etc.). For initial staging of high-risk prostate cancer, this will include a nuclear medicine bone scan and either a CT abdomen and pelvis or MRI of the pelvis per NCCN guidelines. If a patient is determined to be eligible for the, the research coordinator in this study will be asked to come to the clinic to discuss potential enrollment in the study.

4.6 Imaging Information

4.6.1 $[^{18}\text{F}]$ Fluciclovine PET Preparation and Injection

The injected dose will be 370 MBq (10 mCi) of $[^{18}\text{F}]$ fluciclovine. The patient will be instructed to avoid strenuous exercise for 24 hours prior to injection and to avoid caloric intake for 4 hours prior to injection. PET/MRI imaging will begin immediately following injection. Intramuscular injection of glucagon 1 mg will be performed immediately prior to the prostate MRI portion of the PET/MRI.

4.6.2 $[^{18}\text{F}]$ Fluciclovine PET/MRI Protocol

Whole body imaging

Positron Emission Tomography Acquisition: The patient will be placed on the PET/MRI scanner in the supine position. Initial localizer images will be obtained. Dynamic images of the pelvis will be acquired for the first 8 min after fluciclovine injection with framing of 3 sec x 20, 10 sec x 12, 20 sec x 6, 180 sec x 1. Subsequently, static whole body images will be acquired from pelvis to skull base utilizing approximately eight 14 cm detector beds for 5 minute acquisitions per bed position. Correction for randoms, scatter, attenuation and reconstructions will be performed per the manufacturer's recommendations.

Whole Body MRI: Sequences performed will include MR attenuation correction (MRAC), axial and coronal T2 single shot fast spin echo, sagittal T1 turbo spin echo for skeletal evaluation, and whole body Dixon-derived sequences.

Following whole body PET imaging, a routine multiparametric MRI of the prostate gland will be performed at UAB in the PET/MRI scanner per institutional protocol, which includes high b-value diffusion-weighted imaging (b2000), small field-of-view T2 imaging, and dynamic contrast enhanced T1 images. An additional static pelvic PET acquisition will be performed concurrently.

Fluciclovine PET/MRI scans will be performed at two time points:

- Prior to initiation of treatment
- At 3-6 months following treatment initiation when routine clinical practice is to begin assessing PSA values for response

The study protocol has been submitted to, reviewed, and approved by the UAB Radiation Safety Committee.

4.6.3 PET/MRI Imaging Interpretation and Storage

Images from the PET/MRI will be stored and reviewed using a commercially available software package (MIM Encore, Cleveland, OH) and not be available for viewing in the institutional PACS or patient's medical record. This is in an effort to blind the treating physicians from making clinical decisions on an experimental imaging technique. The prostate MRI images will be sent to clinical PACS and the medical record as part of standard-of-care imaging and can be used in the clinical-decision making process. No formal interpretation will be generated for the [¹⁸F]fluciclovine-PET portion of the PET/MRI study, but the prostate MRI will have a clinical interpretation by a dedicated abdominal radiologist who will also be blinded to the patient enrollment in the study. Dedicated study readers from both abdominal imaging and molecular imaging will interpret first the prostate MRI alone, and then the fused PET/MRI to assess potential added value from the PET/MRI. The study readers will be blinded to the results of any additional standard-of-care imaging and clinical evaluation and will only have knowledge that the patient has biopsy-proven prostate cancer.

mpMRI images acquired from the fluciclovine-PET/MRI study will be scored initially without access to the fluciclovine-PET portion of the study using the method described below. Once the results of the MR only portion of the study have been recorded, the same reader will be given access to the entire study and provide a second set of scores for the combined PET/MRI images. The concordance for metastases in lymph node stations will be determined from these scores. At least two readers will score each study, and discrepancies will be recorded and resolved through a consensus read after finalizing individual scoring.

MRI Data Analysis: The MRI images will be qualitatively analyzed.

Qualitative analysis: A visual evaluation of the pelvic lymph nodes with suspected metastatic disease will be performed. The number of positive metastatic lymph nodes and their nodal stations will be recorded. Nodal stations that will be examined include right and left common iliac, internal iliac, external iliac, obturator, inguinal, and retroperitoneal (total of 11 stations per patients).

T1/T2 Images

0 = Normal lymph nodes

1 = Mild prominence not meeting RECIST criteria for adenopathy (low suspicion)

2 = Definitely abnormal size or morphology, possible metastasis (intermediate suspicion)

3 = Markedly abnormal size and morphology, likely metastasis (high suspicion)

DWI Images

0 = Normal diffusion

1 = Low level of diffusion restriction when compared to adjacent normal appearing lymph nodes (low suspicion)

2 = Slightly higher level of diffusion restriction when compared to adjacent normal appearing lymph nodes (intermediate suspicion)

3 = Definitely higher level of diffusion restriction when compared to adjacent normal appearing lymph nodes (high suspicion)

Note: In cases of nonhomogenous intensity on DWI and ADC images, the grade will be determined on the basis of the most suspicious area.

PET Data Analysis: The PET images will be qualitatively and quantitatively assessed. The scoring will be based primarily on the PET data, but the reader will have access to the MRI data for anatomic correlation and characterization of lymph node morphology. For PET data analysis, a lymph node positive based on MRI criteria but negative based on fluciclovine-PET criteria will be scored as negative.

Qualitative analysis: A visual evaluation of the pelvic lymph nodes with suspected metastatic disease will be performed. As per manufacturer guidelines, lymph nodes measuring less than 1 cm in short-axis dimension will be compared to blood pool tracer activity. For lymph nodes measuring greater than 1 cm, comparison of activity will be made to the activity in the bone marrow of the L3 vertebral body. The number of positive metastatic lymph nodes and their nodal stations will be recorded.

0 = No uptake or uptake lower than appropriate reference (blood pool vs. L3 marrow)

1 = Uptake equal to reference (low suspicion)

2 = Uptake slightly greater than reference (intermediate suspicion)

3 = Uptake definitely greater than reference (high suspicion)

Quantitative analysis: Nodes scored as intermediate or high suspicion based on MRI and/or PET will undergo further quantitative analysis.

Standardized uptake values (SUVs): The maximum SUV will be measured. Additionally, the mean SUV and metabolic tumor volume will be measured based on a 40% isocontour.

Lesion to blood pool and marrow ratios: Tissue SUV is a simple uptake ratio of activity in an area of interest compared to a normalized tissue background level. As stated in section B, activity in lymph nodes measuring less than 1 cm in short-axis dimension will be compared with activity in the blood pool and a lesion:blood pool activity ratio will be calculated. For lymph nodes measuring greater than 1 cm in short-axis dimension, activity will be compared to activity in the L3 vertebral body marrow and a lesion:marrow activity ratio will be calculated..

Dynamic PET analysis: Time-activity curves (TACs) will be generated for pelvic lymph nodes scored as intermediate or high suspicion on visual analysis. Additionally, TACs will be generated for three reference pelvic lymph nodes scored as normal. The maximum SUV at peak fluciclovine uptake, the time to peak, and the shape of the TACs over the 8 min dynamic acquisition (rising, plateau, washout) will be recorded. This analysis is exploratory as the role of dynamic fluciclovine-PET for the initial staging of prostate cancer is not established.

KEY ANALYSIS FOR SPECIFIC AIM 1

Based on the consensus PET and MRI scoring, the total percentage of nodal scoring discrepancies will be calculated. Although the total number of patients is small, a total of 165 pelvic nodal stations will be examined. In this pilot study, a discrepancy between MR-only and fluciclovine-PET/MR greater than 10% would motivate a larger study with more rigorous references standards including histopathology.

KEY ANALYSIS FOR SPECIFIC AIM 2

This study will use the nomograms routinely used by the UAB urology service in assessing newly diagnosed prostate cancer. The use of nomograms is necessary, as we will not routinely obtain histopathological verification in these high-risk, nonoperative patients in this study. Expected frequencies of lymph node metastases based on patient risk factors will be compared to observed frequencies of lymph node metastases in specific aim 1 on mpMRI alone, fluciclovine-PET/MRI, and assuming that discrepant nodes between imaging modalities (i.e. positive on one, negative on other) will be counted as positive, a combination of the two modalities that includes discrepant nodes. The assessment that most closely matches the expected frequency based on the nomogram will be considered most accurate, although small sample size will require larger studies for confirmation.

As stated previously, although most patients enrolled in the study will not be surgical candidates, participation in the study does not preclude a patient from surgery. However, given the known value of $[^{18}\text{F}]\text{fluciclovine}$ in the setting of biochemically recurrent prostate cancer and the similar biological tumor profile between treatment-naïve and recurrent prostate cancer, suspicious extraprostatic findings will be reported to the referring physician due to the high likelihood of representing true positive metastatic disease. In these cases, further imaging or biopsy may be indicated prior to proceeding with surgery. The treating physician will initially be blinded to the results of the PET/MRI until a treatment plan is established through the use of standard-of-care imaging, which may include the prostate MRI portion of the PET/MRI but not the fused PET/MRI. Following the treatment decision, the physician will be unblinded to the results of the PET/MRI. Changes in treatment plan based on the PET/MRI will be tracked.

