6.2 Sample Size Determination

This is a pilot study that may warrant a larger study with increased power to determine statistical significance if expected results are observed. We plan to enroll 15 patients, primarily determined by budgetary constraints and feasibility of patient recruitment in one year. No formal power calculations were used in the generation of the sample size. The primary end point of the study is to estimate percentage of high-risk prostate cancer patients whose metastasis can be detectable early by using of [¹⁸F]fluciclovine-PET/MRI comparing using standard care of mpMRI imaging. According to risk-prediction models and nomograms used in routine clinical practice, approximately 20-30% of patients with high-risk prostate adenocarcinoma will be diagnosed with nodal metastases. We expect that using [¹⁸F]fluciclovine PET/MRI will achieve similar results, e.g. 30% for early detection of metastasis without invasive procedures, and using mpMRI will result in less of detection of metastasis, e.g. 20%-25%. A size of 15 will provide a two-sided 95% confidence intervals (CI) for point estimate (% of metastasis) from 9.7% to 58.4% when the true estimate is 30% using Clopper-Pearson method. Table below shows the 95% CI when the true estimate varies.

Proportion (%) (estimate of metastasis)	Sample size	95% CI Lower limit	95% CI Upper limit
20	15	4.3	48.1
25	15	6.9	53.4
30	15	9.7	58.4

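### MRI-only reader disagreements appear to be settled after both readers have seen the PET, so the MRI-only comparator behind the 10% rule is open to PET influence at those stations, in an unknown direction

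*Combined protocol and SAP*

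**What the plan says.** All of the reading procedure is in section 4.6.3 of the combined protocol and SAP. The order of events is:

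1. A reader scores the mpMRI with the PET withheld, and those scores are recorded.
2. Then "the same reader will be given access to the entire study and provide a second set of scores for the combined PET/MRI images".
3. At least two readers do this for every study. Their "discrepancies will be recorded and resolved through a consensus read after finalizing individual scoring".

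The key analysis for Specific Aim 1, later in the same section, uses the output of step 3: "Based on the consensus PET and MRI scoring, the total percentage of nodal scoring discrepancies will be calculated". A discrepancy between MR-only and PET/MR above 10% is named as the result that would motivate a larger study with histopathology.

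Nowhere does the plan describe an MRI-only consensus held before PET access, masking of the PET at the consensus read, or a PET-blind adjudicator. Section 6.4.1 (McNemar test, Spearman correlation) does not say whether individual or consensus scores are analysed.

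**The concern.** Reading MRI first and PET/MRI second by the same reader is an accepted way to measure added value. It depends on the first score being fixed before the second modality is seen. The plan protects that order for each individual reader, but not at the consensus step. Individual scoring consists of both sets of scores, so a consensus held once it is final comes after both readers have seen the PET.

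The stations exposed are those where the MRI was ambiguous enough for two readers to differ, and there knowledge of the PET could sway the decision. The resulting MRI-only consensus enters the pilot's one stated go-forward rule. It also enters Aim 2, which takes the lymph node frequencies on mpMRI alone from Aim 1 and asks which assessment lies closest to the nomogram.

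**Working it through.** **Inputs from the plan**
- Patients: "We plan to enroll 15 patients" (section 6.2). Section 3.6 states that "no replacement of patients will be used", so the full denominator requires all 15 to be evaluable.
- Stations: "total of 11 stations per patients" (section 4.6.3), that is, 5 paired stations × 2 + 1 retroperitoneal = 11.
- Rule: discrepancy above 10%, from consensus scores (section 4.6.3, key analysis for Aim 1).
- Reader-disagreement rate on MRI: not given.

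**Reproducing the plan's figures**
- 15 × 11 = 165 stations, as stated.
- 10% of 165 = 16.5, so the rule is met at 17 or more discrepant stations (17/165 = 10.3%).
- The three Clopper-Pearson intervals in section 6.2 (4.3–48.1, 6.9–53.4 and 9.7–58.4 at n = 15) also reproduce. They are patient-level and do not depend on this point.

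**How steep the rule is near its threshold.** Treat stations as independent, with true discrepancy D. Then P(rule met) = P(X ≥ 17), X ~ Binomial(165, D):

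| D | Expected stations | P(rule met) |
|---|---|---|
| 8% | 13.2 | 17% |
| 10% | 16.5 | 49% |
| 12% | 19.8 | 78% |
| 15% | 24.8 | 97% |

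A change of a few stations can decide the result.

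**Illustration of a PET-aware consensus.** All inputs here are assumptions. Each station is treated as positive or negative. Let q be the share of stations where the readers disagree on MRI. Suppose that under a PET-blind consensus half of these would differ from PET and half would match it. Suppose also that a PET-aware consensus changes the outcome at a share w of the relevant half.

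- Pulled towards PET: D′ = D − q × 0.5 × w
- Pushed away from PET: D′ = D + q × 0.5 × w

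With w = 50%, the net shift is a quarter of the disputed stations (0.5 × 0.5 = 0.25). With D = 12%:

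| q | Shift | D′ towards PET | P(rule met) | D′ away from PET | P(rule met) |
|---|---|---|---|---|---|
| 5% | 1.25 points | 10.75% | 61% | 13.25% | 89% |
| 10% | 2.5 points | 9.5% | 40% | 14.5% | 96% |
| 15% | 3.75 points | 8.25% | 20% | 15.75% | 98% |

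At q = 10% the expected count moves from 19.8 to 15.7 or 23.9, about 4 stations either way.

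**Sensitivity to independence.** Stations in one patient are likely to be correlated. With an assumed within-patient correlation of 0.2 (beta-binomial simulation), P(rule met) is 65% at 12%, 42% at 9.5% and 83% at 14.5%. The swing is smaller but still material.

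**The case against.** **Order of events.** The plan could mean that scoring is finalised one modality at a time, with the MRI disagreements settled before PET is opened. It does not say that PET images are on display at the consensus read, or that MRI and PET/MRI are settled together. This is fair as far as it goes, but no text describes a separate MRI-only consensus. If one was intended, a sentence would settle the matter.

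**Exposure.** It is narrow. Agreed MRI scores are fixed before PET access, and each reader's own MRI scores are kept. The sentence on concordance in section 4.6.3 follows the description of the individual scores and precedes any mention of consensus, so it can be read as using the individual scores. An unaffected analysis is therefore possible from data already collected. All of this stands. However, the percentage compared with 10% is explicitly a consensus figure.

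**Stakes.** This is a descriptive pilot ("No formal power calculations were used in the generation of the sample size"), and the 10% figure is a prompt for further work rather than a test. That limits the severity. The prompt is still what the pilot is meant to deliver.

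Stronger readings are tempting, and the documents do not support them:
- *That the comparator is biased, and towards PET, so that added value is hidden.* Readers might equally settle a doubtful node as MRI-negative because PET shows it, which would inflate the discrepancy. Nothing in the plan fixes the direction.
- *That the effect is as large as 2.5 to 10 points.* This follows if readers disagree at 5–20% of stations (8 to 33 of 165) and half of these (about 4 to 16) are all lost discrepancies. The documents give no disagreement rate. A station disputed on a yes/no score already has one reader on PET's side, and a blind consensus would have matched PET at some of them anyway. Only the remainder can lower the count.
- *That without a between-reader rate the 10% result cannot be told from reading noise.* The comparison is within reader, on the same study. Between-reader agreement is informative but is not its direct error measure.

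**Conclusion.** The point holds as a weakness in the reading procedure. Followed as written, the plan lets PET knowledge into the MRI-only comparator at stations where the readers disagreed on MRI, and the 10% rule is computed from those scores. The result is open to bias; neither the direction nor the size can be established from the documents. The figures under the check only show that plausible shifts could change whether the rule is met when the blind discrepancy lies near the threshold. Further away the rule is more robust: at a blind discrepancy of 15%, the same shift at q = 10% gives 12.5% or 17.5%, and the chance of meeting the rule moves from 97% to 83% or above 99% (independent stations). The stated 165 stations and the section 6.2 intervals are unaffected. The change is worth making before reading starts, because a PET-blind consensus by the same readers cannot be recovered afterwards.

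**What to change.** - In section 4.6.3, state that the readers finalise and lock the MRI-only consensus for a patient before either of them opens that patient's PET, and that the PET/MRI consensus is a separate, later step.
- As a check, report the MR-only versus PET/MRI discrepancy from each reader's own recorded scores beside the consensus figure.
- In section 6.4.1, say which scores, individual or consensus, enter each analysis.
- Between-reader agreement for each modality is optional supporting information.

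The cost is one short extra consensus step per patient, some scheduling so that both readers finish the MRI before either opens the PET, and one extra table. Readers, images and the number of patients do not change.
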